6.1.6 ROUTE OF ADMINISTRATION

The Verapamil HCl will be administered intranasally.

6.1.7 STARTING DOSE AND DOSE ESCALATION SCHEDULE

Phase Ib Verapamil HCl dose will start at a total residual dose of 0.3mg. Dose escalations will be as follows: 0.3mg, 0.6mg, 1.2mg, 2.4mg, 3.0mg, 3.6mg. Participants will remain on a dose for at least one week before escalating.

Phase II dose will be determined by Phase Ib.

6.1.8 DOSE ADJUSTMENTS/MODIFICATIONS/DELAYS

The Phase Ib dose will only be escalated if a participant has not experienced a DLT or 2 ITs on the previous dose. The Phase II dose will not be changed at any point during the 4 week course.

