4 STUDY DESIGN AND ENDPOINTS

4.1 DESCRIPTION OF THE STUDY DESIGN

ARM 1: Phase 1B

The phase IB study will consist of an accelerated titration, intrapatient dose escalation cohort, with double-dose step design. The initial single patient cohort will begin by taking 0.3mg (10mg of Verapamil in 240mL of buffered normal saline yielding an established 3% residual nasal dose) as a nasal irrigation BID for 1 week. The first dose f

each escalation will be administered in a 10th or 11th floor MEE clinic withhemodynamic monitoring. A medically trained member of the study staff with monitor the patient for one hour. Patients will be instructed on the how to properly perform the irrigation using a pre-recorded video demonstration. If no first-course dose limiting toxicity (DLT, defined by the development of 2nd or 3rd degree heart block) is noted then patients will continue taking the current Verapamil rinse dose BID for 1 week. Dose escalation will occur weekly in the absence of a single, any course, DLT or a second, any course, intermediate toxicity(IT, defined by a heart rate of <50, an asymptomatic BP reduction >30% from baseline or systolic BP <90mmHg, an asymptomatic MAP reduction >30% from baseline or MAP<55, an asymptomatic diastolic BP reduction >30% from baseline, and a Meltzer Compliance Grade >4[60]). Each escalation will be a doubling of the dose from 0.3-2.4mg. At that point that dose will escalate in 0.6mg residual intervals for the rest of the trial up to a maximum of 3.6mg total residual dose. These doses were derived from the pharmacokinetic analysis of our oral Verapamil trial results. If a single, any course, DLT or second, any course, IT occurs, two additional patients will be recruited at that identified dose and Phase IB will revert to a standard 3+3 design. If any patient un-enrolls while the dose escalation is still occurring, they will be replaced to maintain 3 patient cohorts. The maximal administered dose(MAD) will be considered that at which at least 2 DLTs or 4 ITs occur and the MTD will then be assigned to the immediate preceeding dose.

At each weekly visit, the patients nasal endoscopy will be recorded for LKS grading, and they will be administered symptom, side-effect, and tolerability questionnaires. Pre-dosing mucus and post-dosing irrigant samples will also be atraumatically collected from the nasal cavity for use in exosomal biomarker sampling.

ARM 2: Phase 2

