5.4 PARTICIPANT WITHDRAWAL OR TERMINATION

5.4.1 REASONS FOR WITHDRAWAL OR TERMINATION

Arm 1: Phase 1B

The PI will terminate a Phase IB participant if they experience a DLT, more than one IT, or begin a contradictory medication during the course of the trial. Patients may withdraw from the trial at any time upon request. Any withdrawn participants from Phase IB will be replaced to maintain 3 patient cohorts. Their reason for withdrawal will be noted.

Arm 2: Phase 2

The PI will terminate a Phase II study participant if they present with any clinical adverse event (AE) or other medical complication such that continued participation in the study would not be in the best interest of the participant. The PI will terminate a participant if they miss more than 2 doses of topical Verapamil in a week. Compliance will be checked using a patient dosing diary. Participants may withdraw from the trial at any time upon request. Any withdrawn participant will be replaced with a new enrollment.

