7.3.3 FOLLOW-UP

Phase 1B:

Participants will asked to fill out a SNOT-22, VAS, , Satisfaction scale, and Compliance scale. Adherence to the treatment regimen will be evaluated. An endoscopy will be recorded and scored. A mucus sample will be collected from the nasal cavity with a small sponge. Participants will be evaluated for side-effects. An EKG will be taken. If no intermediate toxicity or DLT is experienced the participant will be moved up to the next dose. Participants will be asked to perform the initial irrigation of their next dose while being monitored for 1 hour by clinical monitoring equipment. After monitoring the patients will be given a second EKG. The irrigant will be collected. If no EKG abnormalities that are deemed unsafe by the study safety officer are detected during or after the initial irrigation the participants will be prescribed the rest of the verapamil rinse.

Phase 2:

During the Week 1 follow-up visit participants will asked to fill out a SNOT-22, VAS, , Satisscation scale, and Compliance scale. Adherence to the treatment regimen will be evaluated. Participants will be evaluated for side-effects. An EKG will be taken. An endoscopy will be recorded and scored.

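### Phase Ib sets no minimum number of doses for a level to count as tolerated, so a level largely not taken after its supervised first dose can be cleared and feed into the MTD

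*Combined protocol and SAP*

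**What the plan says.** Section 4.1 has the first dose of each level given in clinic with one hour of monitoring. If no DLT (second- or third-degree heart block) follows, "patients will continue taking the current Verapamil rinse dose BID for 1 week". The escalation rule then appears in three places:

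- Section 4.1: "Dose escalation will occur weekly in the absence of a single, any course, DLT or a second, any course, intermediate toxicity".
- Section 6.1.8: "The Phase Ib dose will only be escalated if a participant has not experienced a DLT or 2 ITs on the previous dose".
- Section 7.3.3, Phase 1B: "If no intermediate toxicity or DLT is experienced the participant will be moved up to the next dose".

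The maximal administered dose (MAD) is defined in 4.1 as the level at which "at least 2 DLTs or 4 ITs occur and the MTD will then be assigned to the immediate preceeding dose".

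Adherence is collected. Section 7.3.3 states "Adherence to the treatment regimen will be evaluated", and 6.1.10 and 10.4.5 have staff check a dosing calendar at each visit. Section 5.4.1 lists the Phase Ib reasons for removal: "The PI will terminate a Phase IB participant if they experience a DLT, more than one IT, or begin a contradictory medication". Missed doses are not among them. For Phase II the same section adds "The PI will terminate a participant if they miss more than 2 doses of topical Verapamil in a week", and 10.3 defines a Phase II evaluable set by 80% use of the drug.

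**The concern.** The MTD is the Phase Ib primary endpoint and sets the Phase II dose. A level says something about tolerability only if it was taken. The plan defines clearance by the absence of events and attaches no exposure condition, so the absence of drug and the absence of toxicity are recorded alike.

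Two features sharpen this. Phase Ib opens with a single-patient cohort and intrapatient escalation, so until a trigger occurs one person's week clears a level and the same person carries on upward. Missed doses may also be informative: section 2.3.1 names nasal irritation and constipation as risks, and a participant who finds the rinse unpleasant may skip it, which removes the events the rule looks for. The error tends towards too high an MTD.

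**Working it through.** The plan gives no figure for this point, so the check is a reading of the rules followed by simple arithmetic.

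**Does any rule make exposure count?**

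| Place | Condition on Phase Ib | Doses taken? |
|---|---|---|
| 4.1, escalation | no DLT, no second IT: escalation follows weekly | no |
| 7.3.3, escalation | no IT or DLT: next dose | no, though adherence is evaluated in the same paragraph |
| 6.1.8, escalation | necessary condition on DLTs and ITs | no |
| 4.1, MAD/MTD | at least 2 DLTs or 4 ITs | no |
| 6.1.7 and 6.1.9 | at least one week on the dose | no, elapsed time only |
| 5.4.1, removal | DLT, more than one IT, contraindicated drug | no |
| 10.3, data sets | all Phase Ib patients in the safety set | no |

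Sections 4.1 and 7.3.3 make the absence of toxicity sufficient. Section 6.1.8 does not, but it adds no exposure requirement that would close the gap.

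**Exposure.** Doses per level-week: 2 × 7 = 14, of which 1 is supervised and 13 are taken at home. Supervised share: 1/14 = 7.1%. Phase II removal at more than 2 missed doses leaves at least 12/14 = 85.7% a week. Phase II total: 14 × 4 = 56 doses; 80% of 56 = 44.8, so 45.

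**Size of one wrong clearance.** Write d(k) for the dose at level k (6.1.7: 0.3, 0.6, 1.2, 2.4, 3.0, 3.6 mg). If full exposure would have made level k the MAD, the MTD should be d(k−1). If k is cleared and k+1 proves to be the MAD, the MTD becomes d(k). The overshoot is d(k)/d(k−1):

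- 0.6/0.3 = 1.2/0.6 = 2.4/1.2 = 2.0
- 3.0/2.4 = 1.25

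For 3.6 mg there is no next level. If it is wrongly cleared, I assume it is carried forward in place of 3.0 mg: 3.6/3.0 = 1.2, with no higher level to expose the error.

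**Systemic margin.** Section 2.1 puts the twice-daily intranasal dose equivalent to the oral regimen at 16.8 to 72.75 mg. 16.8/3.6 = 4.7 and 72.75/3.6 = 20.2, so the top residual dose lies 4.7 to 20 times below it.

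**Illustration, on assumptions not in the documents.** Suppose a constant per-dose hazard and a full-week toxicity probability p. After n doses the probability is 1 − (1 − p)^(n/14).

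| p (14 doses) | 1 dose | 7 doses | 12 doses |
|---|---|---|---|
| 20% | 1.6% | 10.6% | 17.4% |
| 33% | 2.8% | 18.1% | 29.1% |
| 50% | 4.8% | 29.3% | 44.8% |

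Under this model one dose reveals little, while 12 doses keep 87% to 90% of the full-week probability (17.4/20, 29.1/33, 44.8/50). If all toxicity is acute and appears at the first dose, nothing is lost at any adherence.

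**The case against.** The best counter-argument is that compliance already enters the rule: a Meltzer Compliance Grade above 4 is an IT, and the scale is completed at every Phase Ib follow-up. Under 7.3.3 a single IT would hold the dose. This narrows the gap without closing it. The documents do not define the scale or tie the grade to doses taken; 4.2.2 treats grades 2 to 3 as mild toxicity, which suggests a tolerability grade. Under 4.1 and 6.1.8 one IT does not stop escalation.

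Other controls exist. Section 6.1.7 requires a week on each dose, 5.5 allows suspension for poor compliance or unevaluable data, 14.3 requires corrective action for deviations, and section 9 has the DSMB review Phase Ib after three participants. These stand as general or discretionary oversight. None says that a largely skipped week does not clear a level.

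It is also fair that the DLT and most ITs are cardiac or haemodynamic, and that each level's first dose has one hour of monitoring and a follow-up EKG. Phase II repeats first-dose monitoring and reviews participants at week 1.

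A reader might infer that 6.1.8 by itself orders escalation after a skipped week. It does not; it says only when escalation is barred. A reader might also infer that the MTD will be too high, or that Phase II participants face a material cardiac risk. The documents support neither: they give no adherence rate, and the systemic margin is wide.

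**Conclusion.** The gap is real and should be closed before Phase Ib starts. Followed as written, 4.1 and 7.3.3 allow a level taken once in 14 doses to be recorded as tolerated, and the MTD tally has no means of discounting it.

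Its frequency cannot be quantified. The one-step overshoot rests on three assumptions: the participant takes too little drug to reveal toxicity, full dosing would have made that level the MAD, and the next level is then correctly identified (or, for 3.6 mg, the top dose is carried forward). For acute toxicity caught at the monitored first dose the effect is nil. Systemic risk is probably small. What remains is mainly intolerance under repeated use, which matters because Phase II then gives the dose up to 56 times. Confidence is medium, because the undefined compliance grade could catch some of these weeks.

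**What to change.** State the following consistently in 4.1, 5.4.1, 6.1.8 and 7.3.3:

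1. Any DLT or IT counts, whatever the adherence.
2. A week without a limiting toxicity counts as tolerated, for escalation and for the MTD tally, only if the dosing calendar shows at least 12 of 14 doses taken. This is the Phase II weekly limit.
3. Otherwise the participant repeats the week at the same dose, which 6.1.7 already permits. If still short, the participant is withdrawn and replaced at that dose, with low adherence added to the Phase Ib removal reasons in 5.4.1.
4. A week cut short by side effects does not count as tolerated. Its events stay in the tally under the existing IT and mild-toxicity definitions, even if the participant leaves. The shortfall should not automatically become an IT: that would redefine an input to the primary endpoint and could promote complaints that 4.2.2 grades as mild.

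The cost is wording in four sections and use of a calendar already collected, plus an occasional extra Phase Ib week (one more visit, with the $150 compensation in 5.3) or a replacement participant.

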6.1.9 DURATION OF THERAPY

Phase Ib participants will undergo therapy for at least 1 week. Total therapy time will be determined by the number of dose escalations a participant is given.

Phase II participants will undergo therapy for 4 weeks.

6.1.10 TRACKING OF DOSE

Participants will fill out a dosing calendar which will be checked by study staff at each visit.

6.1.11 DEVICE SPECIFIC CONSIDERATIONS

N/a

6.2 STUDY AGENT ACCOUNTABILITY PROCEDURES

Verapamil solution for injection and Neil Med sinus rinse will be ordered and received from the Pharmacy's wholesaler Cardinal Health in an amount sufficient to provide dosing in accordance with the subject enrollment. Verapamil and Neil Med sinus rinse will be stored in the pharmacy segregated as stock for this study only

Separate perpetual inventories will be maintained by the Pharmacy on Drug Accountability Logs for both the verapamil and Neil Med sinus rinse (see template log attached). Transactions including receipt of medication, use of medication for compounding dose / dispensation of medication to the subject, and expiration / waste of medication will be documented. In addition, a perpetual line balance indicating the number of containers of medication on hand will be documented.

Verapamil and Neil Med sinus rinse will be dispensed from the Pharmacy for a study subject pursuant to the receipt of a study medication prescription form specific to this project.

7 STUDY PROCEDURES AND SCHEDULE

7.1 STUDY PROCEDURES/EVALUATIONS

7.1.1 STUDY SPECIFIC PROCEDURES

Phase 1B: The below procedures are considered non-standard of care and are study specific:

- Meltzer Satisfaction and Compliance assessment
- Collection of mucus sample from the nasal cavity
- Weekly clinical examination
- EKG

Phase 2: The below procedures are considered non-standard of care and are study specific:

- Meltzer Satisfaction and Compliance assessment
- Collection of mucus sample from the nasal cavity
- FKG

7.1.2 STANDARD OF CARE STUDY PROCEDURES

Phase 1B: The below procedures are considered routine standard of care in the management of patients with CRSwNP:

- Nasal Endoscopy with scoring
- SNOT-22 and VAS assessment for disease severity

Phase 2: The below procedures are considered routine standard of care in the management of patients with CRSwNP:

- Nasal Endoscopy with scoring
- SNOT-22 and VAS assessment for disease severity
- Clinic examination every 2-4 weeks in patients with CRSwNP

7.2 LABORATORY PROCEDURES/EVALUATIONS

7.2.1 CLINICAL LABORATORY EVALUATIONS

Screening: A pregnancy test will be done within 24 prior to the first application of topical verapamil in women of child bearing age.

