5.2 PARTICIPANT EXCLUSION CRITERIA

Patients with the following comorbidities:

- •GI Hypomotility
- •Heart Failure
- •Liver Failure
- Kidney Disease

 Muscular Dystrophy Pregnant or Nursing Females •Systemic Steroid Dependency Hypertrophic Cardiomyopathy •Any Atrial or Ventricular arrhythmia (ie. Atrial fibrillation, atrial flutter, etc..) •Resting Heart Rate less than 60 beats per minute •Baseline Systolic Blood Pressure less than 110 mmHg •Baseline Diastolic Blood Pressure less than 70 mmHg •Baseline Mean Arterial Pressure Less than 60 mmHg •PR interval less than 0.12 seconds Patients taking the following medications: Aspirin Beta-blockers Cimetidine(Tagamet) Clarithromycin(Biaxin) Cyclosporin Digoxin Disopyramide(Norpace) Diuretics Erythromycin Flecainide •HIV Protease Inhibitors(Indinavir, Nelfinavir, Ritonavir) Quinidine •Lithium Pioglitazone

Rifampin

•St Johns Wort

Patients who are unwilling or unable to wash out of systemic steroids

Patients with cardiac or conduction abnormality picked up by screening EKG

Post-op patients with surgery within 3 months prior to enrollment.

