7.3 STUDY SCHEDULE

7.3.1 SCREENING

Phase 1B:

During the screening visit all exclusion/unclusion criteria will be reviewed. If a participant is a good candidate for the study consent will be obtained. Participants will be given an intake questionnaire which queires the presence of a variety of medical parameters which are relevant to the disease process. A pregnancy test will be administered to any female of child bearing age who is sexually active and not using contraception or admits to a possbility of being pregnant. If the participant has used systemic steroids within the past 3 weeks they will be asked to undergo a 3 week washout of steroids before beginning the trial.

Phase 2:

During the screening visit all exclusion/inclusion criteria will be reviewed. If a participant is a good candidate for the study consent will be obtained. Participants will be given an intake questionnaire which queires the presence of a variety of medical parameters which are relevant to the disease process. A pregnancy test will be administered to any female of child bearing age who is sexually active and not using contraception or admits to a pissbility of being pregnant. If the participant has used systemic steroids within the past 3 weeks they will be asked to undergo a 3 week washout of steroids before beginning the trial.

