7.3.2 ENROLLMENT/BASELINE

Phase 1B:

Participants will fill out the baseline questionnaires (SNOT-22, VAS). An endoscopy will be recorded and scored. A mucus sample will be collected from the nasal cavity with a small sponge. Participants will be instructed in the proper method for using the verapamil irrigation. They will then be given a baseline EKG and asked to perform the first verapamil irrigation while being monitored for 1 hour by clinical monitoring equipment and study staff. After monitoring the patients will be given a second EKG. The irrigant will be collected. If no EKG abnormalities that are deemed unsafe by the study safety officer are detected during or after the initial irrigation the participants will be prescribed the rest of the verapamil rinse.

Phase 2:

Participants will fill out the baseline questionnaires (SNOT-22, VAS). An endoscopy will be recorded and scored. A mucus sample will be collected from the nasal cavity with a small sponge. Participants will be instructed in the proper method for using the verapamil irrigation. They will then be given a baseline EKG and asked to perform the

first verapamil irrigation while being monitored for 1 hour by clinical monitoring equipment and study staff. After monitoring the patients will be given a second EKG. The irrigant will be collected. If no EKG abnormalities that are deemed unsafe by the study safety officer are detected during or after the initial irrigation the participants will be prescribed the rest of the verapamil rinse.

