7.3.7 SCHEDULE OF EVENTS TABLE

4	Phase Ib			Phase II			
Procedures	Screening	Enrollment/ Baseline	Weekly/Final Follow-up	Screening	Enrollment/ Baseline	Follow-up (Day 7)	Final Visit (Day 28)
Informed Consent (IC)	X		-	х			
Intake Form (IF)	X	3	į	x		3	
Pregnancy Test (PT)	X			x			
SNOT-22	100	х	х		х	х	X
Visual Analog Scale (VAS)	3	х	x		х	х	X
Electrocardiogram (EKG)		х	х		x	x	
Heart Rate (HR)		х	х		х	х	X
Blood Pressure (BP)	ŝ.	x	x		x	x	х
Lund-Kennedy Score (LKS)		x	x		х	x	X
Nasal irrigation (NI)		х	х		х		х
Mucus sponge (MS)	ý.	x	х		x	- 3	х
Satisfaction Scale (SS)		d	x			Х	х
Compliance Scale (CS)			×			×	х
Side effects (SE)			x			х	X

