8.4.5 REPORTING OF PREGNANCY

Pregnant women will be excluded from this trial. If a participant becomes pregnant during the trial they will be withdrawn and treatment will be immediately halted. The participant will then have safety follow-ups during the course of their pregnancy.

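### Sections 7.2.1 and 7.3.1 disagree on who needs a pre-dose pregnancy test, and no test is listed at the dosing visit, so a woman may be dosed without one

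*Combined protocol and SAP*

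**What the plan says.** Section 7.2.1 (Clinical Laboratory Evaluations), under a Screening label, sets the laboratory rule: "A pregnancy test will be done within 24 prior to the first application of topical verapamil in women of child bearing age". It adds no further condition on who is tested, and the 24 carries no unit in the text as read.

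Section 7.3.1 (Screening) gives the visit instruction, worded alike for Phase 1B and Phase 2: "A pregnancy test will be administered to any female of child bearing age who is sexually active and not using contraception", extended to a woman who admits she may be pregnant. It sets no time limit before dosing. For anyone who has used systemic steroids in the past 3 weeks, it adds that "they will be asked to undergo a 3 week washout of steroids before beginning the trial".

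Section 7.3.2 (Enrollment/Baseline) is where dosing starts: "They will then be given a baseline EKG and asked to perform the first verapamil irrigation while being monitored for 1 hour". The procedures listed there, in either phase, do not include a pregnancy test. In the schedule of events (7.3.7), the pregnancy test row is marked in the same places as informed consent: the Screening column of each phase and nowhere else.

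Section 5.2 excludes "Pregnant or Nursing Females". Section 8.4.5 repeats that pregnant women are excluded and covers a pregnancy found later: "If a participant becomes pregnant during the trial they will be withdrawn and treatment will be immediately halted".

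**The concern.** Pregnancy is an exclusion criterion, and in 7.2.1 the protocol chose to confirm it by a laboratory test before exposure. The visit-level text does not reliably deliver that test. It limits testing to a subset that depends on what the woman reports about sexual activity, contraception and possible pregnancy. It also places the test at a visit that may be well before the first dose.

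The stake is first exposure of an undetected pregnancy to a cardioactive drug. The withdrawal rule in 8.4.5 acts only once a pregnancy is known, so it cannot replace a test before the first dose. This is a matter of participant safety and of consistency between sections. No endpoint, sample size or analysis depends on it.

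**Working it through.** The plan gives no figure to reproduce. The check sets the sections side by side and adds one small piece of arithmetic on timing.

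**Who is tested**

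| Woman of child bearing age who… | 7.2.1 | 7.3.1 |
|---|---|---|
| is sexually active without contraception | test | test |
| says she may be pregnant | test | test |
| uses contraception and does not suspect pregnancy | test | not named |
| is not sexually active and does not suspect pregnancy | test | not named |

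The last two rows are the conflict. Testing everyone satisfies both sections; testing only the group in 7.3.1 breaches 7.2.1. The schedule row carries no population qualifier, so it does not settle which rule governs. This result does not depend on the unit of the 24.

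**When the test is done**

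Inputs: a window of 24 with no unit (7.2.1); a washout of 3 weeks (7.3.1); first dose at Enrollment/Baseline (7.3.2); test marked at Screening only (7.3.7).

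- Full washout: 3 × 7 = 21 days, and 21 × 24 = 504 hours.
- If the window is 24 hours: 504 / 24 = 21, so a test done at the start of a full washout is 21 times older than allowed. Any gap of more than 1 day between test and dose is already too long.
- If the window is 24 days: 21 < 24, so a full washout fits with 24 − 21 = 3 days to spare.

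The delay caused by the washout runs from 0 to about 21 days. It is near 0 if the 3 weeks count from the last steroid use and are almost over at screening, and about 21 days if they count from screening. No maximum interval between screening and baseline is stated, so 21 days is a scenario and not an upper bound.

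**What else could cover the gap**

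Eligibility is reviewed for everyone: "During the screening visit all exclusion/unclusion criteria will be reviewed" (the Phase 2 text says the same). That checks pregnancy by history but does not supply the laboratory confirmation in 7.2.1. In the text available, contraception appears only in 7.3.1, as a trigger for testing. The eligibility criteria (5.1, 5.2) and the precaution and prohibited-treatment sections (7.5.1, 7.6) do not require it. A sexually active woman not using contraception could therefore test negative at screening, complete a washout, and be dosed weeks later with no second test listed.

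**The case against.** The strongest reply is that 7.2.1 already governs. It ties the test to the first application, so if hours are meant, a screening test that has aged out does not satisfy it and another is already required. Dosing without one would be a deviation and not something the protocol permits. On this view, 7.3.2 and the schedule merely fail to repeat an existing requirement. That reading is right, but it does not help at the visit: 7.3.1 and 7.3.2 are the sections staff follow there, and following them as written leads to the breach.

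Other points have weight:

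- The timing part is conditional. It largely disappears if the unit is days or if screening and first dose fall within 24 hours, and the Screening label in 7.2.1 fits the second case. A woman tested at screening has, at worst, an out-of-date test and not no test.
- Section 7.3.1 does not say that its group is the only one to be tested. The women it leaves out are at lower risk and are still asked about pregnancy.
- The design schematic, whose legend includes a pregnancy test, could not be seen. The schedule was read from an extracted table, and the missing unit could be an extraction loss.
- The sections could be aligned the other way, by narrowing 7.2.1 to the rule in 7.3.1. That would remove the inconsistency, but confirmation would then rest on self-report, and the pre-exposure safeguard the protocol already chose would be weakened.
- The protocol does not define child bearing age, so alignment alone leaves the group partly open.

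These points limit the timing part and the size of the problem. None removes the conflict over who is tested.

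**Conclusion.** The concern holds. The two sections name different groups in both phases, and a woman outside the narrower group can receive her first dose with no laboratory pregnancy test if staff work from 7.3.1. This part rests on the text alone.

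The timing part holds only if the 24 means hours and more than 24 hours pass between the screening test and the first dose. A washout can produce that gap, and no repeat test is listed.

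The scale is small. The documents do not give the number of women affected, and the trial plans 20-40 participants of both sexes in all. The correction should be made because it concerns exposure in pregnancy and is cheap; the trial's conclusions are not at risk.

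**What to change.** Apply the rule in 7.2.1 throughout:

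1. In 7.2.1, state the window as 24 hours.
2. In 7.3.1, both phases, replace the narrower group with all women of child bearing age, and add a definition of that term.
3. In 7.3.2 and in the Enrollment/Baseline column of the schedule of events, both phases, add a pregnancy test before the first irrigation. Accept the screening test instead if it was done within 24 hours before the first dose.

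The cost is wording edits in three sections and two schedule cells, plus at most one added inexpensive test per woman of child bearing age among the 20-40 planned participants and any replacements. If the window is hours, this asks for nothing beyond what 7.2.1 already requires.
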